10.4 Data Management and Coding

The CRO will be responsible for data management per their SOPs. This will include setting up a relevant database and data transfer mechanisms, along with appropriate validation of data and resolution of queries. Data generated within this clinical study will be handled according to the relevant standard operating procedures of the data management and biostatistics departments of the CRO.

All data for subjects who sign an ICF and receive a dose of IMP will be recorded via EDC. Subjects who are screened but found ineligible for the study and who do not receive IMP will be considered screen failures. The reason for exclusion from the study will be recorded.

Study centers will enter data directly into the EDC via a secure internet connection. Data entered into EDC must be verifiable against source documents at the study center. Data recorded directly into EDC, if any, will be identified and the EDC will be considered the source document. Any changes to the data entered into the EDC system will be recorded in the audit trail and will be FDA Code of Federal Regulations (CFR) 21 Part 11 compliant.

MedDRA will be used to code AEs. Medications will be coded by WHODrug. Missing or inconsistent data will be noted within the EDC system and queried with the Investigator for clarification. Subsequent modifications to the database will be documented.

11 ETHICAL CONSIDERATIONS AND COMPLIANCE WITH GOOD CLINICAL PRACTICE

11.1 Independent Ethics Committee or Institutional Review Board

Before initiation of the study at each study center, the protocol, the ICF, other written material given to the subject, and any other relevant study documentation will be submitted to the appropriate IEC/IRB. Written approval of the study and all relevant study information must be obtained before the study center can be initiated or the IMP released to the Investigator. Any necessary extensions or renewals of IEC/IRB approval must be obtained for changes to the study such as amendments to the protocol, the ICF or other study documentation. The written approval of the IEC/IRB together with the approved ICF must be filed in the study files.

The Investigator will report promptly to the IEC/IRB any new information that may adversely affect the safety of the subjects or the conduct of the study. The Investigator will submit written summaries of the study status to the IEC/IRB as required. On completion of the study, the IEC/IRB will be notified that the study has ended.

11.2 Regulatory Authorities

Relevant study documentation will be submitted to the regulatory authorities of the participating countries, according to local/national requirements, for review and approval before the beginning of the study. On completion of the study, the regulatory authorities will be notified that the study has ended.

11.3 Ethical Conduct of the Study

The Investigator(s) and all parties involved in this study should conduct the study in adherence to the ethical principles based on the Declaration of Helsinki, GCP, ICH guidelines, and the applicable national and local laws and regulatory requirements.

11.4 Written Informed Consent

The process of obtaining informed consent must be in accordance with applicable regulatory requirement(s) and must adhere to GCP.

The Principal Investigator(s) at each center will ensure that the subject is given full and adequate oral and written information about the nature, purpose, possible risk, inconveniences, and potential benefit of the study. Subjects must also be notified that they are free to discontinue from the study at any time. The subject should be given the opportunity to ask questions and allowed time to consider the information provided. The subject should be given every opportunity to ask for clarification of any points s/he does not understand and, if necessary, ask for more information. The subject will be required to sign and date the ICF. After signatures are obtained, the ICF will be kept and archived by the Investigator in the Investigator's study file. A signed and dated copy of the subject ICF will be provided to the subject. The Principal Investigator(s) must maintain the original, signed ICF.

The Investigator is responsible for ensuring that no subject undergoes any study-related examination or activity before the subject has given written informed consent to participate in the study.

It should be emphasized that the subject may decline to participate in the study and may withdraw from the study at any time without consequences for their further care or penalty or loss of benefits to which the subject is otherwise entitled.

If new information becomes available that may be relevant to the willingness of the subject to continue in the study, a new ICF will be approved by the IEC(s)/IRB(s) (and regulatory authorities, if required). The subject will be informed about this new information and reconsent will be obtained.

11.5 Subject Confidentiality

Monitors, auditors, and other authorized agents of the Sponsor and/or its designee, the IEC(s)/IRB(s) approving this research, as well as that of any other applicable agency, will be granted direct access to the study subjects' original medical records for verification of clinical study procedures and/or data, without violating the confidentiality of the subjects to the extent permitted by the law and regulations. In any presentations of the results of this study or in publications, the subjects' identity will remain confidential.

12 DATA HANDLING AND RECORD KEEPING

All procedures for the handling and analysis of data will be conducted using good computing practices meeting ICH and U.S. Food and Drug Administration (FDA) guidelines for the handling and analysis of data for clinical trials.

12.1 Data quality control and reporting

After data have been entered into the study database, a system of computerized data validation checks will be implemented and applied to the database. Query reports pertaining to data omissions and discrepancies will be forwarded to the clinical Investigator and the Sponsor for resolution. The study database will be updated by the clinical investigator or their staff, in accordance with the resolved query reports. All changes to the study database will be documented.

12.2 Inspection of Records

American Genomics or designee will be allowed to conduct site visits to the investigation facilities for the purpose of monitoring any aspect of the study. The Investigator agrees to allow the monitor to inspect the drug storage area, IMP stocks, drug accountability records, subject charts and study source documents, and other records pertaining to study conduct.

12.3 Records retention

Essential documents are those documents that individually and collectively permit evaluation of the study and quality of the data produced. After completion of the study, all documents and data relating to the study will be kept in an orderly manner by the Investigator in a secure study file. This file will be available for inspection by the Sponsor or its representatives. Essential documents should be retained for 2 years after the final marketing approval in an ICH region or for at least 2 years from the discontinuation of clinical development of the investigational product. It is the

responsibility of the Sponsor or its representatives to inform the study center when these documents no longer need to be retained. The Investigator must contact the Sponsor before destroying any study related documentation. In addition, all subject medical records and other source documentation will be kept for the maximum time permitted by the hospital, institution, or medical practice.

12.4 Amendments to the protocol

Modifications of the signed protocol are only possible by approved protocol amendments and with the agreement of all responsible persons. The procedure for approval of a protocol amendment is identical to that for approval of the protocol. The ethics committee must be informed of all protocol amendments and should be asked for its opinion as to whether a full re-evaluation of the ethical aspects of the study is necessary by the committee. This should be fully documented.

The investigator must not implement any deviation from or change to the protocol, without discussion with, and agreement by American Genomics, LLC and prior review and documented approval/favorable opinion of the amendment from the relevant ethics committee, except where it is necessary to eliminate an immediate hazard to study subjects, or where the change(s) involves only logistical or administrative aspects of the study (e.g., change in monitor(s), change of telephone number(s)).

Protocol amendments will be submitted to the appropriate authority(ies) as required by the applicable regulatory requirement(s).

13 PUBLICATION

The Sponsor must review and approve any results of the study or abstracts for professional meetings prepared by the Investigator(s). Published data must not compromise the objectives of the study. Data from individual study centers in multicenter studies must not be published separately.

Appendix 1: Procedures

For more information, contact the Office of the Vice President for Research and the Office of the Vice President for Student Affairs.

10 of 10 pages

For more information, contact the Office of the Vice President for Research and Economic Development at [contact] or [contact].

19. **What is the primary purpose of the *Journal of Clinical Endocrinology and Metabolism*?**

10. *What is the primary purpose of the following statement?*

11. **What is the primary purpose of the following statement?**

For more information, contact the Office of the Vice President for Research and Economic Development at [contact] or [contact].

[REDACTED]

[figure not shown]
[REDACTED]

[REDACTED]

[REDACTED]

[REDACTED]

[REDACTED]

[REDACTED]

[REDACTED]

[REDACTED]

The image consists of a series of horizontal bars of varying lengths and positions. The bars are mostly black on a white background, with some white bars appearing in the lower half. The bars are arranged in a staggered, non-overlapping pattern, creating a sense of depth or a digital signal. The lengths of the bars vary significantly, with some being very short and others extending across the width of the frame. The positions of the bars are not uniform, with some appearing in the upper half and others in the lower half. The overall effect is a high-contrast, abstract pattern that could represent a digital signal or a specific type of data visualization.

[REDACTED]

[REDACTED]

[REDACTED]

[REDACTED]

[REDACTED]

[figure not shown]
[REDACTED]

Procedures: Urine

Urine pregnancy tests will be performed on all women of childbearing potential at Visit 1 (prior to treatment).

## ABBREVIATIONS AND DEFINITIONS

AE	Adverse Event
ANOVA	Analysis of Variance
ANCOVA	Analysis of Covariance
BCVA	Best Corrected Visual Acuity
CMH	Cochran Mantel Haenszel
CI	Confidence Interval
CRF	Case Report Form
ET	Early Termination
ITT	Intention to Treat
IOP	Intra-Ocular Pressure
LOCF	Last Observation Carried Forward
MedDRA	Medical Dictionary for Regulatory Activities
OD	Oculus Dexter (Right Eye)
OS	Oculus Sinister (Left Eye)
PK	Pharmacokinetics
PP	Per protocol
SAE	Serious Adverse Event
SD	Standard Deviation
SOC	System Organ Class
TEAE	Treatment Emergent Adverse Event

## 1 INTRODUCTION

### 1.1 Trial Objectives

The primary objective of this study is to evaluate anesthetic efficacy of AG-920 administered by topical ocular route as compared to placebo.

The secondary objectives of this study are:

- To evaluate the onset of anesthetic effect of AG-920, i.e., how long it takes one dose of two drops 30 seconds apart of AG-920 to anesthetize the eye;
- To evaluate the duration of anesthetic effect of AG-920, i.e., how long the anesthetic effect lasts in the eye following one dose of two drops 30 seconds apart of AG-920;
- To evaluate the safety and tolerability of AG-920 administered by topical ocular route.

This document describes the statistical analysis methods and data presentations for the data analyses of Protocol AG920-CS302. Related documents to this SAP are the study protocol and case report form (CRF or eCRF). Data analysis will be based on the final dataset(s) provided by Sponsor or designee Data Management group, which is InFocus Clinical Research.

The study database(s) includes all of the CRF-based clinical data and all of central laboratory data. The original EDC database constructed by InFocus Clinical Research will be converted into CDISC SDTM version 3.1 and/or 3.1.1 database. InFocus Clinical Research will provide the treatment code for treatment unblinding after database lock.

### 1.2 Background Information

Injections of pharmacologic agents into the vitreous cavity for the purpose of treating various disorders of the retina as well as intraocular inflammatory disease have become the mainstream. In almost all cases, these injections are made through the pars plana. An injection into the eye in this location, with the needle oriented properly, will be posterior to the human lens or an intraocular implant, but anterior to the retina, thereby avoiding damage to these important structures. The pars plana is a zone that rings the eye extending from 3.0 mm to 5.5 mm from the edge of the cornea.

While topical agents such as proparacaine achieve excellent anesthesia on the external surface of the eye, they do not numb the internal aspect of the pars plana, which is extremely sensitive. Currently, physicians fall into one of two methodologies: either injecting lidocaine under the conjunctiva first and then executing a second injection through the pars plana, or by using topical lidocaine gel and then performing the intravitreal injection. Patients often report moderate to severe discomfort with each of these approaches. Thus, it is important that a new tool is developed for physician to use in assisting the intravitreal injection.

For that purpose, American Genomics is evaluating the formulation of articaine, an approved local anesthetic, for topical ocular use to provide local anesthesia for intravitreal injections. The Sponsor intends to develop Articaine Sterile Topical Ophthalmic Solution (coded named AG-920) for topical ocular use to induce local anesthesia for intravitreal injection. [REDACTED]

[REDACTED]

In summary, AG-920 is a sterile topical ophthalmic solution made from articaine for physicians to apply on the pars plana area of the eye to assist performing the intravitreal injection of pharmacologic agents for the treatment of various disorders of the retina.

## **2 STUDY DESIGN**

### **2.1 Rationale**

The AG-920 topical drop would allow a technician to apply the topical solution to the eye, allow the articaine to penetrate the pars plana sufficiently to permit the intravitreal injection without undue discomfort. AG-920 is selected for this procedure based upon being made from Articaine which has clinical use in dental procedures, suggesting it penetrates soft tissue and bone.

### **2.2 Description of Trial Design**

This is a Phase 3, randomized, placebo-controlled, double-masked, parallel-group design study of safety and anesthetic efficacy of AG-920 topical drop versus placebo in healthy subjects. The study will evaluate the safety and anesthetic efficacy following one dose of Articaine Sterile Topical Ophthalmic Solution (AG-920), in comparison with placebo. Eligible subjects will be randomized in a 1:1 ratio to receive a single dose of AG-920 or matching placebo into one eye, designated as subject's study eye. The application of one single dose of AG-920 involves two drops 30 seconds apart into the subject's study eye.

The study consists of two visits and a follow-up phone call: one screening visit on Day -2 (Visit 1), one baseline/assessment visit on Day 1 (Visit 2), and one follow-up phone assessment on Day 2-5 (Phone Follow-Up).

Following the screening visit, eligible subjects will return to the clinic on Day 1 to have their study eye randomly assigned (right eye=OD or left eye=OS) and to be randomized to receive the study medication into the study eye. Subjects will undergo a conjunctival pinch procedure, and the pain associated with the pinch will be rated. Dosing of the study medication and conjunctival pinch procedure will be performed by the study staff.

To assess the anesthetic effect of the study medication, all subjects will be pinched at 20, 40, 60 seconds and 5 minutes post dose, defined as after the second drop of the dose application. If the subject feels no pain at 5 minutes, the subject will be considered "anesthetized." Pinching of anesthetized subjects will resume at 10 minutes and pinching will continue every five minutes for up to 30 minutes or until pain resumes. If the subject experiences pain 5 minutes post dose, pinching will be concluded and this subject will be considered to NOT have reached anesthesia.

All subjects who are randomized and who receive the study medication on Day 1 will be followed up with a phone call to on Day 2-5 for safety assessment.

### **2.3 Schedule of Assessments**

The complete schedule of assessments for this entire study is shown in Table 1 of the study protocol (see Protocol No. AG920-CS302 Amendment 1, Page 10).

The effects of anesthesia is assessed, following the application of study medication, by conjunctival pinch procedure on the study eye and verbal asking of pain from the subject at

20, 40, 60 seconds and 5 minutes after the second drop as well as every five minutes afterward.

#### **2.4 Randomization**

As stated in the protocol, randomization schedule generated by the Sponsor or designee will be used to assign subjects to each of the two treatment groups with a 1:1 allocation ratio to receive AG-920 drops or matching placebo.

Study medication will be pre-packaged into individual medical product application packs with one pack being used per application according to the randomization schedule. All of the medical product packs will be identical in appearance except that each pack bears a unique randomization number (or kit number). The prepackaged packs will be shipped to a study site once the first subject is screened at the site and re-shipments of the supplies will be sent to a site as needed during the study.

Each eligible subject will be assigned to one of the prepackaged packs available at a site. The kit number associated with the prepackaged pack will be recorded on the CRF for this subject. Actual treatment assignments will be masked to the Investigator, the clinical study team (Sponsor, personnel involved in day to day study management, Monitors, Data Managers, and Statisticians), and the subjects.

Only in case of medical emergency or occurrence of adverse events that warrant unmasking in the opinion of the Investigator, will the treatment assignment(s) be unmasked and made available to the Investigator and the Sponsor Safety Officer. In the absence of medical need, the randomization code will not be available to the above personnel until after the study is completed and the database is locked.

#### **2.5 Sample Size Estimation**

The study is intended to test for a difference in proportion of subjects with anesthetic response (i.e., no pain) between AG-920 and placebo at 5 minutes post dose.

Assuming a 25% delta in proportion between AG-920 and placebo groups and an anesthetic response (i.e., no pain at 5 minutes post dose) to placebo of 15%, a sample size of 60 per group will provide a statistical power of 88% at the significance level of 0.05 (2-sided), with a Chi-square test without continuity correction.

Therefore, a total of 120 subjects randomized with an equal allocation ratio (1:1) of the active versus placebo will be needed in the present study.

#### **2.6 Efficacy and Safety Measurements**

In this study, primary efficacy endpoint will be assessed using the proportion of subjects with anesthetic response defined as no pain by conjunctival pinch at 5 minutes post application of the dose. The secondary efficacy endpoints will be: 1) the onset of anesthetic effect defined as the time to no pain by conjunctival pinch within 5 minutes post application of the dose; and, 2) the duration of anesthetic effect defined as the time from the onset of anesthetic effect to the time point when pinch pain resumes.

Safety will be assessed through subject early terminations, adverse events, best corrected visual acuity (BCVA), biomicroscopy and external eye exam, and concomitant medications.

### **2.6.1 Primary efficacy measure**

The primary efficacy endpoint for this study is the proportion of subjects with anesthetic response defined as no pain at 5 minutes post application of the dose. Pain is assessed using conjunctival pinch procedure. Dosing of the study medication and conjunctival pinch procedure will be performed by the study staff.

To assess the anesthetic effect of the study medication, all subjects will be pinched at 20, 40, 60 seconds and 5 minutes post dose application. If the subject feels no pain at 5 minutes, the subject will be considered "anesthetized." Pinching of anesthetized subjects will resume at 10 minutes and pinching will continue every five minutes for up to 30 minutes or until pain resumes. If the subject experiences pain 5 minutes post dose application, pinching will be concluded and this subject will be considered to NOT have reached anesthesia.

### **2.6.2 Secondary efficacy measure**

The secondary efficacy endpoints include the following:

- Time in minutes to no pain within 5 minutes post application of the dose defined as post the 2nd drop of the dose. Once a subject achieves no pain or anesthetic effect, the time to the onset of anesthetic effect will be calculated as the time interval in number of minutes between the time of dose application completion and the time point when the first observation of no pain is recorded. All timepoints post dose will be converted to minutes so the 20, 40 and 60 second timepoints will be 0.33, 0.67 and 1.0 minutes, respectively. For those subjects who drop out after dose application without achieving anesthesia or who do not achieve the anesthetic effect within 5 minutes post dose, the time to the anesthetic effect will be considered being censored at the last assessment of pinch test or at 5 minutes (censored time point), whichever occurs earlier.
- Duration in minutes from the onset of anesthetic effect to the time point when pinch pain resumes. For those subjects who have achieved an anesthetic effect post dose, the duration of anesthetic effect is calculated by subtracting the anesthetic effect onset time from the time of the first observation of pinch pain return. For those subjects who did not achieve an anesthetic effect post dose, this duration is not applicable and will be set to missing.

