2 OBJECTIVES AND ENDPOINTS

Primary Objective

To evaluate anesthetic efficacy of AG-920

Secondary Objectives

To evaluate how long it takes one dose of AG-920 to anesthetize the eye

To evaluate how long one dose of AG-920 anesthetizes the eye

To evaluate the safety and tolerability of AG-920

Primary Endpoints

The proportion of subjects with no pain at 5 minutes.

Secondary Endpoints

Mean time to no pain score (onset)

Mean duration of anesthetic effect

Visual acuity, biomicroscopy, AEs, TEAEs, SAEs, withdrawals due to TEAEs

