6.4.3 Post Treatment and Pinch Test

- [REDACTED] forceps will be used to “pinch” the [REDACTED] conjunctiva of the study eye at the following timepoints. Details on the pinching method will be provided separately:
 - **20 seconds following complete dose administration** (second drop of IMP)
 - **40 seconds following dose administration**
 - **60 seconds following dose administration**
 - **5 minutes following dose administration**
- Immediately following EACH pinch test, subjects will be asked “Was that painful” “Yes” or “NO.” It should be explained to subjects that the feeling of pressure is NOT to be judged as pain. [REDACTED]
[REDACTED].

All subjects are pinched at 20, 40, 60 seconds and 5 minutes post dose. If the subject feels no pain at 5 minutes, the subject will be considered “anesthetized.” Pinching of anesthetized subjects will continue at 10 minutes and EVERY FIVE MINUTES for up to 30 minutes or until pain resumes. Once pain resumes, pinching is stopped.

If the subject experiences pain at 5 minutes, pinching will be concluded and this subject will be considered to NOT have reached anesthesia at 5 minutes.

Within 15-60 minutes after the last pinch test, the following examinations will be performed

- BCVA
- Perform slit lamp biomicroscopy and external eye exam
- Assess for adverse events
- Schedule Follow-up Phone Call between Day 2-5 (1-4 days following dosing).

Windows: Times will be measured to the nearest minute with the exception of the 20, 40 and 60 second time points. Those should be recorded to the second. Times up to 5 minutes post 2nd instillation should be followed. Investigators are allowed a window of \pm 1 minute at the 10 minute time point, and \pm 2 minutes at subsequent time points.

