#### Onset of anesthetic effects

The secondary endpoint of the onset of anesthetic effect in minutes from time of dose application completion to no pain within 5 minutes post dose is defined in Section 2.6.2. This endpoint will be compared for between-group differences, using a 2-way ANOVA model with treatment (the effect of interest) and study eye side as the effects. The study-eye-side effect is used as a blocking factor in the model to control the potential treatment differences among the study eye sides. For the accuracy and appropriateness of the analysis, those subjects who are censored on (or not achieving) the onset of anesthetic effect will be excluded from statistical analysis.

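### Onset is known only to the interval between pinches, yet the SAP averages pinch times as exact, so the mean depends mainly on the share of achievers first pain-free at 5 minutes

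*SAP*

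**What the plan says.** Protocol 6.4.3 sets the schedule: "All subjects are pinched at 20, 40, 60 seconds and 5 minutes post dose". SAP 2.6.1 agrees: "all subjects will be pinched at 20, 40, 60 seconds and 5 minutes post dose application". Neither document places a pinch between 60 s and 5 min. Protocol 6.4.3 gives timing windows only from the 10-minute pinch onward, so planned variation in timing does not fill the gap.

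Protocol section 2 names the secondary endpoint as a mean ("Mean time to no pain score (onset"). SAP 2.6.2 measures onset from completion of the dose to "the time point when the first observation of no pain is recorded", and fixes the early values: "All timepoints post dose will be converted to minutes so the 20, 40 and 60 second timepoints will be 0.33, 0.67 and 1.0 minutes". The only on-schedule value left is 5.0.

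For the analysis, SAP 2.9.2 says: "This endpoint will be compared for between-group differences, using a 2-way ANOVA model with treatment", with study eye side as the other effect. Subjects who do not reach onset are described as censored in 2.6.2 and then left out of the analysis in 2.9.2. Neither section treats an achiever's onset as known only to lie between two pinches.

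Duration (SAP 2.6.2) is the time of pain return minus this onset. Pain return is observed on a coarser grid: "Pinching of anesthetized subjects will continue at 10 minutes and EVERY FIVE MINUTES for up to 30 minutes or until pain resumes".

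**The concern.** The secondary objective is how long one dose takes to numb the eye. A subject who becomes numb at 61 s and one who becomes numb at 4 min 59 s, both still numb at 5 min, receive the same score of 5.0. The first three scores can be late by at most 0.33 min, while the last can be late by up to 4 min. The mean and the ANOVA difference are therefore governed by how many achievers fall in the last category and by the number attached to it. Moving the last pinch would change both with no change in drug effect. A mean in minutes would look like a measured time to anesthesia, which the data cannot supply.

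**Working it through.** **Inputs.** Pinches at 20, 40, 60 s and 5 min (Protocol 6.4.3, SAP 2.6.1). Scores of 0.33, 0.67, 1.0 and, by the same rule, 5.0 min (SAP 2.6.2). Achievers only in the ANOVA (SAP 2.9.2). 60 per group, 15% placebo response and a 25-point difference for the primary endpoint (SAP 2.5). The documents give no onset distribution, so the shares below are assumptions shown over a range.

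**The plan's own figure.** No power or precision is stated for onset. The primary power reproduces. With 15% v 40%, the pooled proportion is 0.275, and z = [0.25·√60 − 1.96·√(2·0.275·0.725)] / √(0.15·0.85 + 0.40·0.60) = (1.936 − 1.238)/0.606 = 1.15. Power is 0.8755, against 88% stated. Nothing below changes it.

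**Step 1: what each score means.**

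| Score (min) | Interval containing onset | Largest lateness (min) |
|---|---|---|
| 0.33 | (0, 0.33] | 0.33 |
| 0.67 | (0.33, 0.67] | 0.33 |
| 1.0 | (0.67, 1] | 0.33 |
| 5.0 | (1, 5] | 4.0 |

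**Step 2: size.** Let f be the share of achievers first pain-free at 5 min, with the rest split equally over the first three pinches (average score (0.33 + 0.67 + 1.0)/3 = 0.67).

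- Recorded mean = 0.67(1−f) + 5f
- Lowest true mean compatible with the same data = 0.33(1−f) + 1·f
- Largest overstatement = 4f + 0.33(1−f)

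| f | Recorded mean | Lowest compatible mean | Largest overstatement |
|---|---|---|---|
| 0 | 0.67 | 0.33 | 0.33 |
| 10% | 1.10 | 0.40 | 0.70 |
| 25% | 1.75 | 0.50 | 1.25 |
| 50% | 2.83 | 0.67 | 2.17 |

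Each 10 percentage points of achievers moved from the 1.0 to the 5.0 score adds 0.40 min to the mean, wherever in the gap their onset fell.

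**Step 3: the between-arm difference.** With f = 10% in one arm and 25% in the other, the recorded difference is 1.75 − 1.10 = 0.65 min. If every onset came at the start of its interval, it would be 0.50 − 0.40 = 0.10 min. Small numbers add to this: at the planned 15% response, placebo has 0.15 × 60 = 9 responders. If these are the achievers, one subject moving from 1.0 to 5.0 shifts the placebo mean by 4/9 = 0.44 min.

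**Step 4: illustration only.** Assume exponential onset times with numbness lasting to 5 min, and take subjects with onset by 5 min. For an exponential mean of 1 min, the interval shares are 0.285, 0.204, 0.147 and 0.364. The scored mean is 0.285·0.33 + 0.204·0.67 + 0.147·1 + 0.364·5 = 2.20 min, against a true 0.97. For exponential means of 0.25, 0.5, 2 and 3 min, scored v true is 0.52 v 0.25, 1.13 v 0.50, 3.13 v 1.55 and 3.48 v 1.84 min.

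**Step 5: duration.** Onset scored up to 4 min late shortens duration. Pain return, scored late on the 5-minute grid, lengthens it. The two errors partly offset, and the documents do not allow a net figure.

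**The case against.** Four points have force.

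- *Much of the reporting already exists.* Protocol 9.4.1 promises counts and percentages by treatment and time point for categorical assessments, which covers percent pain-free at each pinch. SAP 2.9 gives a median beside the mean, and SAP 4.5.1 lists individual pinch responses. Table shells and the figure list are redacted. This stands, so it would be wrong to infer that the plan reports only a mean. But percentages at a pinch are not cumulative proportions, the median covers achievers only, and the inferential method in SAP 2.9.2 is still the ANOVA.
- *A rank test would be immune.* True: recoding 5.0 as 1.01 leaves the ranks unchanged. But SAP 2.9 adds non-parametric results only if non-normality is substantial, and alongside the ANOVA.
- *Both arms share one masked schedule.* So the scoring alone does not favor either arm when the drug has no effect. This also stands. The problem is the meaning and size of the mean and its difference.
- *SAP 2.6.2 already defines onset as the first recorded pain-free observation.* It does, so the mean is a valid time of first pain-free pinch. The gap opens when it is read as time to anesthesia.

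Two stronger readings are tempting. One is that any onset in the 4-minute gap scores 5.0. Numbness that starts and ends within the gap is never seen, so this holds only if it is still present at 5 min. The other is that the recorded mean will be about twice the true one. That comes from the exponential assumption, and no document gives an onset distribution.

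**Conclusion.** The concern holds for the secondary onset endpoint. On schedule, the scored onset has four possible values, and the SAP treats them as exact times in an ANOVA among achievers. The mean and the ANOVA difference depend mainly on f. The largest overstatement of the mean is 4f + 0.33(1−f): 0.33 min if every achiever is pain-free by 60 s, and 0.70, 1.25 and 2.17 min at f = 10%, 25% and 50%. The bound needs only the pinch grid and f. The recorded means also assume an equal split over the first three pinches. These are maxima, not estimates, and if nearly all achievers are pain-free by 60 s the issue is small.

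A reader might infer that the superiority claim is at risk. It is not: SAP 2.9.1 and Protocol 9.4.6 rest it on the proportion pain-free at 5 min, which does not use onset scores. Duration inherits the onset error, partly offset.

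A related point needs settling. SAP 2.6.1 counts a subject in pain at 5 min as not having reached anesthesia, while the rule in SAP 2.6.2 would give that subject an onset if an earlier pinch was pain-free.

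**What to change.** In SAP 2.6.2 and 2.9.2, before unmasking:

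1. Make the between-group onset comparison an interval-censored (or ordinal/rank) analysis of all ITT subjects. Use intervals (0, 0.33], (0.33, 0.67], (0.67, 1] and (1, 5], with subjects who have no pain-free pinch right-censored at their last pinch or 5 min, whichever is earlier. This also brings back the non-achievers that 2.9.2 excludes.
2. Report for each arm the cumulative proportion with a first pain-free pinch by 20 s, 40 s, 60 s and 5 min, and the interval containing the median if it is reached. With planned 5-minute responses of 15% and 40%, it may not be reached in either arm.
3. State how subjects who are pain-free early but in pain at 5 min are counted for onset, and reconcile 2.6.1 with 2.6.2.
4. If the mean is kept because the protocol names it, present it descriptively as the mean time of the first pain-free pinch among achievers, an upper bound on onset.

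The cost is SAP wording and one table, with no new pinches or data. The small downside is that onset is stated as an interval rather than a single mean.
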